and data analysis and submit publications for peer review. These time estimations are plans that could be subject to change based on a number of external factors that may be out of our control. We plan to follow each subject clinically for a minimum of 24 months following implant, and to follow them for 12 more months for a minimum of 2 and a maximum of 4 research visits, and then clinically each year as long as they wish to remain implanted, and to assess needs for battery replacement. We plan to apply to CMS and Medicare for insurance coverage of the device implantation and battery replacement costs, and to apply to Medtronic for device donation (Medtronic has already reviewed this proposal in their scientific grants committee and approved donation of the devices and replacement devices).

6) Protocol: Methodology to be used - The study will be a prospective blinded design. Subjects will include ten individuals with medication refractory and severely disabling TS. We expect to consent and screen 50 individuals in order to enroll ten. A total of 6/10 subjects (60%) will need to be “responders” as a result of the intervention (YGTSS motor tic subscale reduction of $\geq 40\%$) for this study to reach effectiveness criteria.

Inclusion Criteria

- The diagnosis of TS must be made by both a fellowship-trained movement disorders neurologist and a psychiatrist and must meet Diagnostic and Statistical Manual of Mental Disorders (DSM-V) criteria for a diagnosis of TS.
- Yale Global Tic Severity Scale (YGTSS; 100) must be $\geq 35/50$ for at least 12 months and the motor tic subscore ≥ 15 . The TS must be causing incapacitation with severe distress, self-injurious behavior, and/or quality of life disruption.

OCD, Depression, and ADHD are not exclusionary[63-65] provided tics are the major difficulty requiring surgical intervention.

- There are no gender criteria for this study.

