- The primary safety outcome will be defined as the serious adverse event (SAE) rate in patients compared to the SAE rate in patients implanted with the Medtronic DBS device for treatment of Parkinson's disease as drawn from published randomized studies[13, 67-71]. The intent is to show that the serious adverse event rate will not exceed the 95th percent confidence interval for the historical experience with the Medtronic DBS for Parkinson's disease. A 95% confidence interval for the SAE rate will be utilized for an analysis of data for 10 subjects at their three month visits due to the small sample size.
- The secondary outcome measure will consist of a review of the types, duration and frequency of non-serious adverse events. Therefore, all adverse events will be used as an additional measure in determining safety outcomes.
- The safety experience will be reviewed approximately every 6 months by the Data Safety Monitoring Board (DSMB). The DSMB will be informed of all serious adverse events and all mild adverse events which are potentially device related. The DSMB will designate each AE as mild or severe; as device related, uncertain to be device related or not device related; and as anticipated or unanticipated. The DSMB may employ a stopping rule for greater than 1 device related death or completed suicide.

Details of the Protocol:

- Following consent, subjects will be screened by the multidisciplinary team

and ethics panel to be certain all inclusion and exclusion criteria are met.

- Following approval by the multidisciplinary and ethics panel, subjects will undergo baseline studies and within four weeks will receive bilateral CM devices and bilateral ECOG devices.
- Stimulation will be turned on within one week (+/- 7 days) after the implant completion which will be approximately one month post lead implantation.
- All subjects will undergo once a month programming visits for months 1-6 (+/- 14 days, with the exception of Month 1, which has a +/- 7 day window). Additional visits may be needed to obtain optimization of settings.

Physiological data will be collected from both the CM thalamus and the ECOG strips during all protocol visits, and responsive parameters will also be tested. Subjects may also choose to come to the clinic for “unscheduled visits” as they deem necessary. The activities done at these visits will be at the discretion of the principal investigator.

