Data Safety Monitoring Board (DSMB): This study will have a designated DSMB composed of three members (A neurologist, a psychiatrist, and a non-neurological physician) without ties to the current study or any conflicts of interest. The DSMB will be charged with the duty of meeting every 6 months to discuss all of the AE's for the study.

The safety experience will be frequently reviewed by the Data Safety Monitoring Board (DSMB). The DSMB will be informed of all serious adverse events and all mild adverse events which are potentially device related in the opinion of the investigator. The DSMB will designate each AE as mild or severe; as device related, uncertain to be device related or not device related; and as anticipated or unanticipated.

Once the first subject is enrolled, the DSMB will meet approximately every 6 months in person, via teleconference, or electronically until all subjects have completed the 6

month primary outcome. The DSMB has the authority to suspend further enrollment pending investigation of safety concerns raised by SAEs occurring in the trial. The DSMB has a stopping rule for more than one death or more than 1 suicide deemed to be device related. The DSMB stopping rule for an individual subject would be a suicide attempt deemed potentially device related.

Adverse Event Reporting: Once a subject is enrolled into the study, continuous close monitoring will be conducted by the Principal Investigator (PI) in conjunction with the neurosurgeon and other investigators as well as the University of Florida's Institutional Review Board (IRB), through annual reports of progress and by immediate notification of serious and unanticipated adverse events by the PI to the IRB.

Stopping rules for the study have been established: This study will be suspended by the DSMB only if an unexpected and severe psychiatric or neurological complication occurs and they deem suspending or stopping the study appropriate. Specific examples that would warrant suspending the study include the following, only in the event that they do not reverse with adjustment or discontinuation of the DBS device:

- Severe worsening of symptoms
- Induction of severe difficult to treat depression

Additionally, the DSMB has a firm stopping rule for more than a single death or suicide attempt in the cohort during the 6 month post-operative period.

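### Sections 12 and 17 state the trial-level stopping rule for deaths and suicidality inconsistently in force, qualifying event, attribution and period

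*Combined protocol and SAP*

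**What the plan says.** The combined protocol and SAP addresses stopping in two sections.

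- **Section 12, Study Summary** (the bullet on DSMB review): "The DSMB may employ a stopping rule for greater than 1 device related death or completed suicide".
- **Section 17, Monitoring Procedures, DSMB paragraph:** "The DSMB has a stopping rule for more than one death or more than 1 suicide deemed to be device related". The next sentence covers the single participant: "The DSMB stopping rule for an individual subject would be a suicide attempt deemed potentially device related". The same paragraph gives the board a general power: "The DSMB has the authority to suspend further enrollment pending investigation of safety concerns raised by SAEs occurring in the trial".
- **Section 17, paragraph on stopping rules for the study:** "This study will be suspended by the DSMB only if an unexpected and severe psychiatric or neurological complication occurs", joined to the condition that "they deem suspending or stopping the study appropriate". The two examples given are non-fatal: severe symptom worsening and severe depression, in either case not reversed by adjusting or discontinuing the device.
- **Section 17, last sentence of that part**, introduced by *Additionally*: a "firm stopping rule for more than a single death or suicide attempt in the cohort during the 6 month post-operative period".

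Both sections also say that the DSMB classifies each adverse event as device related, uncertain, or not device related.

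**The concern.** A stopping rule is useful because it is fixed before the events. The board should be able to read off whether the condition is met and whether it still has a choice. Here, deaths and suicidality are covered by several statements that do not match. Section 12 is permissive, one paragraph of section 17 states a rule as existing, and another calls its rule firm. Completed suicide qualifies in two places and attempted suicide in a third. Device-relatedness is a condition in two and is not mentioned in the third. Only one has a time window.

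Section 17 itself says that the project entails substantial risk, and section 5 relies on stopping rules for subject safety. If two qualifying events occurred, the board, the investigator and the IRB could each cite a different sentence, and the governing rule would have to be settled after the outcome was known.

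**Working it through.** The documents give no event rate, probability or operating characteristic for these rules, so there is no figure to reproduce. The check is to set the statements side by side and apply each to the same events.

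**Step 1. The statements compared**

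| | Section 12 | Section 17, DSMB paragraph | Section 17, last sentence |
|---|---|---|---|
| Force | *may* | *has* | *firm* |
| Event | death, completed suicide | death, suicide | death, suicide attempt |
| Attribution | device related | device related | none stated |
| Period | none stated | none stated | 6 months post-operative |
| Count | more than one | more than one of either | more than one; pooling unclear |

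The complication clause in section 17 is a separate trigger. It is discretionary and worded as exclusive (*only if*).

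**Step 2. The same events under each statement**

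| Events | Section 12 | Section 17, DSMB paragraph | Section 17, last sentence |
|---|---|---|---|
| Two device-related deaths, Month 4 | met, optional | met | met, firm |
| Two device-related deaths, Month 9 | met, optional | met | outside window |
| Two non-fatal suicide attempts, Month 3 | not covered | not covered at trial level | met |
| Two deaths not device related, Month 4 | not met | depends on reading | met |
| One device-related death and one attempt, Month 4 | not met | not met | depends on reading |
| One attempt, Month 3 | not covered | not covered at trial level | depends on reading |

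The first three rows do not depend on how ambiguous wording is resolved. The first shows the difference in force, the second the difference in period, and the third the difference in event.

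**Step 3. Where the result depends on reading**

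- *Attribution.* In the DSMB paragraph the device-related qualifier follows suicide and may or may not reach back to deaths. That decides the fourth row. In section 12 it precedes death and may or may not reach forward to suicide. Neither place says how an event classified as uncertain counts.
- *Pooling.* In the firm rule, one death plus one attempt meets the threshold if the two types are added together, but not if each needs its own count above one. If the threshold applies to deaths alone, a single attempt is enough. That decides the last two rows.
- *Level.* An attempt possibly due to the device is an individual-subject matter in one paragraph, while attempts of any cause are a trial-level trigger in the next. The two can coexist, but how they relate is not stated.

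**Step 4. The exclusive wording**

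Read literally, *only if* would rule out suspension for a death that is neither a psychiatric nor a neurological complication, and it makes every suspension discretionary. That does not fit a firm rule. It also sits awkwardly with the broader power to suspend enrolment over concerns raised by any SAE.

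**Step 5. How much follow-up the window leaves out**

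Section 12 sets follow-up at 24 to 36 months after implantation. Outside the firm rule's window lie 24 − 6 = 18 months to 36 − 6 = 30 months per subject. Section 5 staggers implantation over four years (2 + 3 + 3 + 2 = 10 subjects), and section 17 has the DSMB meeting until all have reached the 6-month outcome. Early subjects will therefore be well past their own six months while the board is still sitting.

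**The case against.** The strongest reply is that different triggers are not contradictory. A stopping rule says when to stop, and an unmet trigger does not tell the board to continue. Read as alternatives, two attempts within six months meet the firm rule, and two device-related deaths at Month 9 meet the other two statements, so both cases have an answer. Section 12 and the DSMB paragraph may be one rule stated twice. The complication clause concerns non-fatal deterioration, and *Additionally* most naturally adds the firm rule to it.

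Much of this stands. A reader might infer from the third row that two attempts stop the study under section 17 while section 12 requires it to go on. The documents do not support that, because section 12 is silent on attempts. Nor do they support the inference that subjects would be unprotected while the wording is unsettled. There is an individual-subject rule, a general power to suspend enrolment, a suicidality scale at every visit, and immediate notification of serious and unanticipated events to the IRB. Nothing in the documents gives a rate of attempts either, so any stated chance of reaching the threshold would be invented.

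The reply does not remove the difference in force. Even if all triggers are cumulative, two device-related deaths after Month 6 come under a rule that the board *may* employ in section 12 and *has* in section 17. Within six months the same events are also under a firm rule, and nothing says which statement governs. The protocol never says that the triggers are cumulative, and the cumulative reading leaves attribution and pooling unresolved.

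**Conclusion.** The point holds as an inconsistency in stated safety rules. Sections 12 and 17 differ on the force of the rule, on the qualifying event and its attribution, and on the period. The exclusive wording of the complication clause fits neither the firm rule nor the power to suspend enrolment, although *Additionally* may have been meant to make the firm rule a further trigger.

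The clearest instance is two device-related deaths within six months: discretionary in one place, firm in another. This conclusion rests on the text alone and needs no assumed event rate. It does not extend to saying that the sections order contrary actions, and it makes no judgement on which rule is clinically right.

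**What to change.** Reconcile sections 12 and 17 into one statement of the trial-level rule, placed in section 17 and cross-referenced from section 12. It should give:

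- the event types that count (attempted or completed suicide, deaths);
- whether device-relatedness is required and for which events, whose classification decides, and how an uncertain classification counts;
- whether deaths and suicidality events are pooled, and the count that triggers the rule;
- the period, per subject or for the whole study;
- whether stopping is mandatory or at the DSMB's discretion;
- whether the triggers are cumulative, including the complication clause;
- how the rule relates to the individual-subject rule.

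Remove *only if*, or align it with the single rule and with the DSMB's authority to suspend enrolment. The sponsor and DSMB choose the content. The cost is a wording amendment, with no added patients, visits or analyses.

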phase. Prior to home testing, patients will be instructed on how to exit adaptive mode at any time and return to open-loop mode should excessive discomfort occur, but are encouraged to consult with study staff if possible prior to doing so.

Summit RC+S sensing malfunction or premature battery drainage: Should the sensing capability of Summit RC+S fail, without failure of the therapeutic stimulation function, we will attempt to restore it by noninvasive restoration of the software (see design master file for Summit RC+S referenced in this application). Should the sensing function be permanently lost with no compromise of the therapeutic function, no specific treatment is needed, and the patient would exit from the study. Regarding the possibility of premature depletion of battery life due to use of the sensing function in addition to the neurostimulation function, this risk is mitigated by the fact that the sensing function utilizes relatively little energy (compared to therapeutic stimulation). Within its lifetime labeled for 9 years, RC+S has no known limit to the number of times it can be recharged.

Manufacturing Information: Please reference Medtronic MAF 2978, PMA P960009 and P840001 for information on these devices.

Device Charges: The Investigational Device, including the Summit RC+S system, will be provided by Medtronic.

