- Physiology data beyond month 12, and the chronic stimulation titration (visits 6.1-6.4), may be performed at the participant’s home as necessary rather than at the University of Florida. The equipment used are all mobile as shown in the RC+S system configuration as explained in Section 18 (refer to Figure 3).
- Details of physiology collection procedure: The subject will be asked to put on EMG sensors and signals from this device will stream into the research host computer (RHC). The signals from the Summit RC+S device will also be downloaded onto the RHC, which will have the Summit Research

Development Kit (RDK) installed (refer to Section 19). Stimulation and brain activity data since the previous visit can then be reviewed and analyzed on an individual basis.

- The CM neurostimulators will be programmed in an outpatient setting to deliver only chronic continuous stimulation in all patients. Stimulation parameters will be adjusted as necessary to provide maximal tic reduction. The cortical strips will be chronically set to record mode for data collection only, until the acute Aim 3 responsive trial.
- The neurologist and DBS programmer will be allowed to adjust stimulation parameters during months 1-5 to achieve maximal tic suppression and minimal to no side effects. The programming that will be employed will be identical to that used for Parkinson's disease randomized trials[13, 67-71].
- At day 180 (6 months +/- 14 days), the primary and secondary outcome variables will be collected, as will all scales. If optimization is not achieved at Month 6, Month 6 data collection may be postponed as deemed necessary by the Principal Investigator (with the exception of the C-SSRS), up to 12 months (+/- 14 days) past the first programming visit (Month 1). However, there must be a 30 period of stable stimulation settings before primary outcomes are assessed.
- Primary and secondary outcomes and physiology collection will be assessed over approximately 3 outpatient days. The "on" DBS condition will be used and compared to the pre-operative baseline for the primary outcome (specific aim 1). The other conditions will be used for secondary analyses, and the on

responsive stimulation response will be compared to the pre-operative baseline (specific aim 3).

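### A subject whose RC+S permanently loses sensing must exit the study even with therapy intact, although Aim 1 effectiveness and safety do not depend on sensing

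*Combined protocol and SAP*

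**What the plan says.** Section 19 (System Overview), in the paragraph on sensing malfunction and premature battery drainage, sets out two steps. If sensing fails while therapy continues, "we will attempt to restore it by noninvasive restoration of the software". If the loss proves permanent and therapy is not compromised, "no specific treatment is needed, and the patient would exit from the study".

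The Aim 1 procedures are in section 12 (Study Summary and Details of the Protocol):

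- Stimulation: "The CM neurostimulators will be programmed in an outpatient setting to deliver only chronic continuous stimulation in all patients". The cortical strips only record until the Aim 3 test.
- Effectiveness: the on-stimulation state is the one of which the plan says this "DBS condition will be used and compared to the pre-operative baseline for the primary outcome". The endpoint is the blindly rated YGTSS at six months. That assessment may be postponed by up to 12 months after the Month 1 programming visit.
- Safety: a 95% confidence interval for the serious adverse event rate is used "for an analysis of data for 10 subjects at their three month visits due to the small sample size".
- Research follow-up lasts 24 to 36 months after implantation.

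Section 6 sets the success rule: "A total of 6/10 subjects (60%) will need to be" responders. Section 13 plans ten subjects and states no dropout allowance.

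Under Specific Approaches for Aim 3, a subject with no usable tic predictor simply gets no chronic responsive setting. Exit is not required.

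**The concern.** The exit rule applies to a subject who is still receiving the Aim 1 treatment and can still be rated on the Aim 1 scale. Such a subject can no longer contribute new physiology (Aim 2) or responsive stimulation data (Aim 3). Nothing in Aim 1 has changed for them.

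The rule also sits oddly beside the treatment of subjects without a predictor. They too cannot contribute chronic responsive data, yet they stay in the study.

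In a trial of ten, each early exit is a visible share of the primary analysis. The sections on statistics and outcomes do not say how an exited subject counts in the six-of-ten rule, or whether the subject is replaced. Research follow-up also stops in a subject who carries an investigational system with a known fault. Section 14 states that no patient had yet received this RC+S and cortical-strip combination for Tourette syndrome.

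**Working it through.** **1. Which outcomes need sensing**

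| Component | Needs sensing? |
|---|---|
| YGTSS, on stimulation at Month 6 versus baseline (primary) | No |
| Serious adverse event rate at Month 3 (primary safety) | No |
| On versus off comparison at Month 6 (secondary) | No |
| Physiology recording (Aim 2) | Yes |
| Responsive stimulation (Aim 3) | Yes |

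**2. What is lost, by time of exit**

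| Exit | Primary safety | Primary effectiveness | Longer research follow-up |
|---|---|---|---|
| Before Month 3 | cut short | lost | lost |
| Month 3 to the primary assessment | kept | lost | lost |
| After the primary assessment | kept | kept | remainder lost |

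**3. The plan's own power figures**

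Inputs from section 13: null 0.10, alternative 0.60, alpha 0.05. Table 2 gives 0.80, 0.75 and 0.70 for 10, 9 and 8 patients. These match a one-sided two-sample formula with n per arm and mean proportion 0.35:

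power = Φ{[0.50 − 1.645 √(2 × 0.35 × 0.65 / n)] / √[(0.10 × 0.90 + 0.60 × 0.40) / n]}

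- n = 10: (0.5 − 0.3509) / 0.1817 = 0.821, power 0.794
- n = 9: (0.5 − 0.3699) / 0.1915 = 0.680, power 0.752
- n = 8: (0.5 − 0.3923) / 0.2031 = 0.530, power 0.702

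That formula is not the one-arm exact binomial test planned for Aim 1. This is a separate matter. Table 2 is used here only as the plan's own scale, on which each early exit costs about 5 points.

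**4. The six-responder rule**

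If six responders are still needed, or equivalently an exited subject counts as a non-responder among ten, the chance of success is P(X ≥ 6), X ~ Binomial(n, 0.60):

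- n = 10: 0.2508 + 0.2150 + 0.1209 + 0.0403 + 0.0060 = 0.633
- n = 9: 0.2508 + 0.1612 + 0.0605 + 0.0101 = 0.483
- n = 8: 0.2090 + 0.0896 + 0.0168 = 0.315

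**5. Other readings of the threshold**

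- Table 2 lists 5 responders for both 9 and 8 patients. With 5 as the pass mark, P(X ≥ 5) is 0.733 (n = 9) and 0.594 (n = 8). That column equals 0.60 × n rounded (5.4 and 4.8), so it may be an expected count and not a pass mark.
- Exact one-sample test against 0.10, with 0.025 in the upper tail (4 responders needed at each n): power 0.945, 0.901 and 0.826 for n = 10, 9 and 8.

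**6. Safety precision**

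With no serious adverse events, the exact upper 95% limit is 1 − 0.025^(1/n): 30.8%, 33.6% and 36.9% for n = 10, 9 and 8. This applies only to exits before Month 3.

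**7. How likely is an exit?**

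The documents give no sensing-failure rate. The table assumes a per-subject risk q of permanent loss before the primary assessment, and gives the chance of at least one exit, 1 − (1 − q)^m, with m subjects exposed:

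| q | m = 10 | m = 4 |
|---|---|---|
| 2% | 18% | 8% |
| 5% | 40% | 19% |
| 10% | 65% | 34% |
| 20% | 89% | 59% |

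The m = 4 column supposes that the six patients whose earlier-device (PC+S) data are mentioned in section 19 are among the ten. The documents do not confirm this.

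**The case against.** The strongest reply is that this is a narrow contingency in a study where two of three aims need sensing. Much of that reply stands:

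- Exit follows only after software restoration fails and the loss is permanent, not after any sensing fault.
- Most of the 24 to 36 months of follow-up falls after an on-time Month 6 assessment. A loss in that period leaves both primary analyses intact.
- The steep fall to 0.483 and 0.315 needs the threshold to stay at six. The plan does not say which threshold applies after an exit, and on the Table 2 scale the loss is about 5 points per subject.
- The rule is written for the RC+S, so subjects implanted with the earlier device may not be exposed.
- The text just before this paragraph was not available for review. A lead-in limiting the rule to one part of the study cannot be excluded, although the plain words refer to the study.

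A reader might also infer three stronger things that the documents do not support. First, that data already collected are thrown away: nothing excludes data gathered before exit. Second, that follow-up ends altogether: the consent section, section 12 and the options for subjects after the aims are complete all promise clinical visits for the life of the battery. These are standard-of-care visits, so what stops is structured research follow-up. Third, that the safety result is biased in the device's favour: nothing links loss of sensing to later serious adverse events, and the malfunction itself can still be reported.

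None of these limits gives an Aim 1 reason for the exit.

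**Conclusion.** The concern holds in a conditional form. As written, the rule ends Aim 1 and research safety data collection in a subject whose treatment and outcome assessments do not depend on the failed function. It is also out of line with how subjects without a predictor are handled.

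The primary analyses are affected only if exit comes before Month 3 (safety and effectiveness) or before the Month 6 assessment (effectiveness). One or two such exits reduce the plan's stated power from 0.80 to 0.75 or 0.70. If six responders are still required, they reduce the chance of success at a true 60% rate from 0.633 to 0.483 or 0.315. The expected loss cannot be stated, because neither the failure rate nor the number of subjects exposed is given. This is an avoidable loss that should be corrected. It is not evidence that the trial's result would be biased.

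**What to change.** In section 19, replace the exit clause with wording such as: *the subject stops the sensing-dependent Aim 2 and Aim 3 procedures but remains in the study for all scheduled Aim 1 assessments and adverse-event follow-up, and is counted among the ten.*

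The change concerns study participation and data collection only. It alters no stimulation setting or treatment decision, and the subject may still withdraw at any time.

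The cost is one sentence and slightly more data collection at visits already in the schedule. The documents do not show whether every cost of those visits is funded, so the sponsor should confirm this.
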